This study builds on a body of preliminary work speaking to HRVB's potential as an addendum to first-line SUD treatments. We will be using the 'Lief Smart Patch' device in this research (<https://getlief.com>). The Lief Smart Patch is a small, wearable, electrocardiogram (ECG)-based heart rate monitor that is attached to the body utilizing skin safe ECG electrodes. ECG technology is known to be safe and carries no substantial risk. The device monitors heart rate variability (HRV) as an index of autonomic nervous system arousal and can prompt the wearer to engage in brief bursts of HRVB practice via a connected smartphone app when stress is inferred. Wearers are also able to engage in regularly scheduled HRVB practice, and practice *ad libitum*. The Lief biofeedback device is being used in this study to deliver a clinical intervention and collect physiological data; the effectiveness of the device itself is not being tested.

2. Specific Aims and Objectives

The aim of this pilot study is to administer heart rate variability biofeedback (HRVB) to adults with substance use disorder who are receiving outpatient treatment as usual (TAU) and compare them to a control group receiving TAU only on intervention outcomes that include alcohol/drug use and negative affect. The study's specific aims are as follows:

[figure not shown]
- Aim 1:** Assess ambulatory HRVB's uptake by individuals with SUD in terms of practice time, and perceived barriers to uptake based on qualitative participant feedback (proof-of-concept)
- Aim 2:** Test effects of HRVB practice on affect and substance use
 - a.** Test day-level effects of HRVB practice on affective states and substance use
 - b.** Test the accumulative, person-level effects of scheduled daily HRVB practice vs. in-the-moment HRVB practice, vs. their interaction on substance use during the 8-week intervention period

We hypothesize that participants receiving HRVB + TAU will have a lower alcohol/drug use lapse rate and demonstrate greater reductions in negative affect compared to controls receiving TAU only.

3. General Description of Study Design

Design Overview

We will recruit 120 adults with substance use disorder (SUD) in their first year of a current SUD recovery attempt. Participants will be randomized using the SAS statistical program to either the experimental ($n= 70$) or control group ($n= 50$). We will also recruit 10 experimental group participants to participate in focus groups ($n= 5$ in each).

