Experimental group participants will participate in 8 weeks of HRVB training using the Lief HRVB biopatch and smartphone app, and 2x daily ecological momentary assessment of affect and substance use. Participants will also be encouraged to self-initiate ecological momentary assessment surveys when feeling high levels of stress or craving. Experimental group participants will be encouraged to wear the Lief HRVB biopatch for at least 8 hours per day and use it as needed to regulate negative affect in-the-moment with a minimum of 5mins daily *ad hoc* practice, and 5min of scheduled HRVB practice twice daily, for a total of 15min daily practice.

The control group will participate in 8 weeks of 2x daily ecological momentary assessment of affect and substance use. Participants will also be encouraged to self-initiate ecological momentary assessment surveys when feeling high levels of stress or craving. Both groups will be allowed to continue with whatever SUD treatment they are independently engaged in. In other words, we will not ask participant to desist any existing treatments they are utilizing.

4. Subject Selection

Participants

Participants will be 120 adults ≥ 18 years of age in the first year of a current SUD recovery attempt. To reduce the likelihood of acute substance withdrawal symptoms influencing affect and physiological indices, participants will be required to have at least two weeks of abstinence from alcohol and other drugs immediately prior to study participation. To allow for recruitment of a representative sample of individuals in early recovery from SUD, commonly co-occurring psychological conditions such as affective disorders and PTSD will be allowed. Medications will be allowed. However, individuals with severe cardiac arrhythmias which would confound HRV

analyses will be excluded, as will persons with active psychosis.

Recruitment Procedures

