6. STUDY PROCEDURES

On the study intake Zoom call, after providing informed consent (~10min), participants will complete a series of questionnaires via a secure REDCap link provided in the Zoom chat-box (~45min). Following this, participants will be guided through the process of installing the TigerAware ecological momentary assessment app on their smartphone and instructed how to use it (~5min). Finally, for experimental group participants, the researcher will provide the study rationale and give brief instruction in paced breathing (~30min). Immediately following the intake call, the experimenter will arrange for a Lief device to be mailed to the participant by Lief Therapeutics, which will come with instructions for setting up the device and downloading the accompanying smartphone app.

To maximize ecological validity in this study, the same HRVB phone coaching offered to regular Lief subscribers will be available to the experimental group participants. The Lief coaches are experts in HRVB and can help with any technical issues with the equipment or queries pertaining to the participant's HRVB practice. Coaches will reach out to study participants to schedule a 20-minute onboarding call when the Lief equipment is ordered. During the orientation call, the Lief coach will cover the following topics:

- Why HRV matters for your mental and physical health
- How Lief's HRV tracking and biofeedback training will help you achieve your health and wellness goals

- How to do a Downtime practice (a.k.a. HRV biofeedback exercise)
- Understanding how Lief's autodosing program works
- The coach's role: *"As your coach, I will support you as a sensemaker of your data to optimize your use of the Lief so we help you self-regulate your stress response more effectively"*
- Communication expectations: Mostly in the app chat box, I'll respond on weekdays. Schedule 20-minute calls every 2 weeks in the app so we can review your progress together.

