Using multilevel models where days (L1) are nested within persons (L2), we will explore the effects of day-level HRVB practice earlier in the day (i.e., lagged) on subsequent day-level negative affect (**Model 1**), craving (**Model 2**), positive affect (**Model 3**), and substance use (yes/no; **Model 4**), while also testing whether HRVB decouples the anticipated relationship of day-level negative affect (**Model 5**) and craving on subsequent substance use (**Model 6**).

In models 1-3 (multilevel linear regression models), the dependent variables will be day-level negative affect scores, day-level craving scores, and day-level positive affect scores, with lagged day-level minutes of scheduled practice, and lagged in-the-moment HRVB practice (with controls' HRVB practice coded as 0), and their interaction term (lagged scheduled practice \times lagged in-the-moment practice) as the independent variables, controlling for age, sex, nicotine use (yes/no), medications known to affect the cardiovascular system (yes/no), and baseline past-month AOD use (percent days abstinent).

A priori, we anticipate that both greater daily scheduled HRVB practice and in-the-moment HRVB practice will predict lower subsequent day-level negative affect and craving, and that their interaction will indicate additive benefits of combining scheduled and in-the-moment practice. The relationship between positive affect and HRVB has not previously been explored, so we will treat this aspect of the analysis as exploratory. Our benchmark for preliminary demonstration of treatment benefit will be semi-partial R²'s for practice time of $\geq .10$ (medium effect size).

Models 1-3

Negative affect = day-level scheduled HRVB practice_{t-1} + day-level in-the-moment HRVB practice_{t-1} + [day-level scheduled HRVB practice_{t-1} * day-level in-the-moment HRVB practice_{t-1}] + age + sex + nicotine use + medications known to affect the cardiovascular system + baseline past-month AOD use + error

Craving = day-level scheduled HRVB practice_{t-1} + day-level in-the-moment HRVB practice_{t-1} + [day-level scheduled HRVB practice_{t-1} * day-level in-the-moment HRVB practice_{t-1}] + age + sex + nicotine use + medications

*known to affect the cardiovascular system + baseline past-month AOD use
+ error*

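### The hypothesis is a greater reduction in negative affect, but no planned analysis measures change from a pre-intervention level; the cost is mainly precision, and one survey at intake would recover part of it

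*Combined protocol and SAP*

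**What the plan says.** The affect hypothesis in Section 2 is comparative and concerns change: the HRVB arm will "demonstrate greater reductions in negative affect compared to controls receiving TAU only".

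Section 3 gives each arm an 8-week EMA period and mentions no run-in: "The control group will participate in 8 weeks of 2x daily ecological momentary assessment of affect and substance use", and the experimental arm has the same surveys alongside its training. Section 9 (Aim 2a) builds the negative and positive affect indices separately for each EMA survey, with craving also examined alone. No pre-intervention value is defined for any of them.

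For the analysis, Section 9 states: "In models 1-3 (multilevel linear regression models), the dependent variables will be day-level negative affect scores", with craving and positive affect as the other two outcomes. The predictors are lagged scheduled practice, lagged in-the-moment practice and their product, with controls set to 0. The covariates are age, sex, nicotine use, cardiovascular medication and baseline past-month percent days abstinent. Baseline affect, earlier affect, time and group do not appear.

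Model 7, by contrast, adjusts percent days abstinent for its own baseline value. A version with group as the predictor is stated for Models 4 to 7, but not for Models 1-3.

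At the intake call (Section 6), "participants will be guided through the process of installing the TigerAware ecological momentary assessment app on their smartphone and instructed how to use it". Breathing instruction for the experimental arm comes after this, and the device is posted later.

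**The concern.** A reduction is a difference from a starting point, and the plan defines no starting point on the scale of the outcome. The baseline covariate carried through Models 1-3 belongs to the substance-use outcome and is at best a proxy for affect. Its range is also narrow. Section 4 requires two weeks of abstinence just before entry, so over a 30-day month the value cannot fall much below 14/30 = 47%.

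Section 4 admits people with affective disorders and PTSD, so stable differences between people in usual affect are likely to be large. Without a baseline they stay in the person-level variance and widen the interval around any comparison between arms or between people. This matters because Section 9 says that power is limited and that effect sizes from this pilot will inform the next trial.

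**Working it through.** **The plan's own figure.** Section 9 claims more than 99% power for Models 1-6 with r = 0.15, 8,300 observations, 5% alpha and conditional independence. By Fisher's z (two-sided), atanh(0.15) × √8,297 − 1.96 = 0.1511 × 91.09 − 1.96 ≈ 11.8, so power is essentially 1. The figure reproduces on its stated assumption. It concerns practice effects across surveys, and this point neither disputes it nor depends on it.

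**Is an arm contrast biased without a baseline?** In a simulation of 20,000 randomised trials at 70:50, with a true arm effect of −0.40 SD and an assumed baseline-to-follow-up correlation of 0.6:

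- difference in follow-up level: mean −0.401, SE 0.185;
- difference in change from baseline: mean −0.399, SE 0.166.

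Both recover the true value. They differ in precision.

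**How much precision would one baseline survey add?** The inputs are:

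- surveys per person: up to 84 (Section 9);
- arms: 70 and 50 (Section 3);
- person-level intraclass correlation of the index (ICC): assumed 0.3 to 0.6;
- correlation ρ between a person's true level at baseline and over the 8 weeks: assumed 0.5, 0.7 or 1.

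With total variance 1, the variance of the person mean is ICC + (1 − ICC)/84. Its squared correlation with one baseline survey is r² = (ICC × ρ)² / [ICC + (1 − ICC)/84]. The standard error is multiplied by √(1 − r²).

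Example at ICC 0.3 and ρ 0.7: variance = 0.3 + 0.7/84 = 0.3083; r² = 0.0441/0.3083 = 0.143; √0.857 = 0.926, a 7% smaller SE.

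| ρ | r², ICC 0.3 | r², ICC 0.6 | SE reduction |
|---|---|---|---|
| 0.5 | 0.07 | 0.15 | 4% to 8% |
| 0.7 | 0.14 | 0.29 | 7% to 16% |
| 1 | 0.29 | 0.60 | 16% to 36% |

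**In terms of power.** Take an assumed arm difference of 0.5 SD of the person mean. The unadjusted SE is √(1/70 + 1/50) = 0.185, so 0.5/0.185 − 1.96 = 0.74 and power is 77%. At ρ = 0.7 the SE is multiplied by 0.926 (ICC 0.3) or 0.842 (ICC 0.6), and power becomes 83% or 89%.

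**Effect on the practice coefficients.** Assume a random intercept per person. Between-person information then has relative weight (1 − ICC)/[(1 − ICC) + 84 × ICC]. This is 0.7/25.9 = 2.7% at ICC 0.3 and 0.4/50.8 = 0.8% at ICC 0.6. If 50-70% of the variance in practice lies between people (assumed), the between-person share of the practice coefficient runs from 0.008 × 0.5/(0.008 × 0.5 + 0.5) ≈ 0.8% to 0.027 × 0.7/(0.027 × 0.7 + 0.3) ≈ 6%. A baseline covariate acts on that small share only.

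**The case against.** A reader might infer that the trial cannot estimate a reduction at all, or that a lower level in the HRVB arm cannot be told apart from a lower starting point. The documents do not support that. Section 3 specifies randomisation: "Participants will be randomized using the SAS statistical program to either the experimental" or the control group. Expected starting levels are therefore equal, and the expected arm difference in level equals the expected arm difference in reduction. Chance imbalance is already reflected in the standard error. This objection stands.

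A reader might also infer that no affect reading exists before the intervention. That is not established. Intake includes about 45 minutes of questionnaires whose instruments are not named, so an affect scale can be neither confirmed nor excluded. The app is installed on the call, whereas "Immediately following the intake call, the experimenter will arrange for a Lief device to be mailed to the participant by Lief Therapeutics", so some surveys may precede device practice. These points stand in part. No model uses an intake affect score, the start of EMA counting is not stated, and no early surveys are reserved as a baseline. Surveys after the call would also follow the breathing instruction in the experimental arm.

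A third inference is that stable differences in affect seriously bias the practice effects. With a random intercept, the between-person contribution is small, as shown above. Nor would a single baseline covariate remove within-person confounding of practice by affect on the same day.

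The time-varying effects model in Section 9 describes how the HRVB association changes during the trial. It does not supply a pre-intervention level.

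The most telling objection is that the precision gain applies to an arm contrast that Models 1-3 do not explicitly contain. Section 9 refers to main effects of group in general terms, but a group version is written out only for Models 4 to 7. A baseline covariate alone would leave the hypothesis without its test, so the two changes belong together.

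**Conclusion.** The concern holds as a mismatch between hypothesis and analysis, with a cost in precision. It is not a failure of identification. No planned analysis estimates change in affect from a pre-intervention level, and Models 1-3 adjust for the baseline of a different outcome.

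For an arm or person-level contrast, one baseline survey would reduce the standard error by about 7-16% at ρ = 0.7 and about 4-8% at ρ = 0.5. The 16-36% range requires perfectly stable true affect and should not be relied on. These figures rest on an assumed ICC of 0.3 to 0.6 and on a survey taken during a call behaving like an ordinary EMA survey. The documents give no value for either correlation. The within-person lagged-practice coefficients would barely move.

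**What to change.** - **Collect a baseline.** When the EMA app is installed at intake, have every participant complete one EMA survey as the practice survey, before the breathing instruction and before allocation is disclosed. Section 5 mentions randomisation ahead of consent and leaves the order unclear, so the sequence should be written down. A reading taken after participants know their arm could be coloured by it.
- **Use it.** Enter the matching score as a covariate: negative affect in Model 1, craving in Model 2, positive affect in Model 3. Past-month percent days abstinent can stay.
- **State the arm comparison.** Add a group version of Models 1-3, as is already done for Models 4 to 7, and report the arm effect as a baseline-adjusted difference.
- **If enrolment is too advanced.** Use an affect scale from the intake questionnaires, if one was collected. Otherwise reword the hypothesis as lower negative affect during the 8 weeks.

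The cost is one or two minutes in a session where the app is already being taught, and one covariate per model. The drawback is that a single reading is noisy and is taken in a call setting.

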Participants will be recruited via Mass General Brigham HealthCare's RSVP for Health Recruitment system, as well as flyers placed throughout Mass General Brigham Healthcare sites (e.g., Massachusetts General Hospital, Brigham and Women's Hospital, McLean Hospital). Advertisements will also be placed on social media sites such as *In the Rooms* and *Facebook* with chat and comment features disabled in order to protect privacy. Individuals who are interested in participation will be invited to call the study researchers who will explain the study procedures in detail, including the potential benefits and risks and the expected duration and time commitment of their participation. Potential participants will also be able to complete a brief, online, pre-screening questionnaire delivered via REDCap. Individuals who are potentially eligible based on their responses to this form will be contacted by study staff for full phone screening (see 'Subject Enrollment' section below).

5. Subject Enrollment

Individuals interested in participating in the study will complete a brief phone interview (~10min) to determine their study eligibility. Those deemed eligible will be scheduled for a virtual study intake session conducted over a Mass General Brigham Zoom and will be randomized to either the experimental (HRVB + TAU) or control group (TAU only). On the study intake Zoom call, participants will be invited to provide informed consent using the REDCap e-Consent Module.

The consent form will include language indicating experimental group participants will be invited to participate in a focus group following the 8-week course of HRVB.

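### The aim tests HRVB added to outpatient treatment, but entry does not require treatment and no model includes it, so the enrolled contrast is not guaranteed to be HRVB + TAU versus TAU

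*Combined protocol and SAP*

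**What the plan says.** **Aim and contrast.** Section 2 states the aim as giving HRVB to "adults with substance use disorder who are receiving outpatient treatment as usual (TAU) and compare them to a control group receiving TAU only". The hypothesis uses the same contrast: "We hypothesize that participants receiving HRVB + TAU will have a lower alcohol/drug use lapse rate". Section 5 applies the labels HRVB + TAU and TAU only to everyone found eligible and randomized.

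**Who may enter.** Section 3 says: "We will recruit 120 adults with substance use disorder (SUD) in their first year of a current SUD recovery attempt". Section 4 repeats this with an age limit, "Participants will be 120 adults ≥ 18 years of age in the first year of a current SUD recovery attempt", and adds that "participants will be required to have at least two weeks of abstinence from alcohol and other drugs immediately prior to study participation". It excludes severe cardiac arrhythmia and active psychosis. Neither section makes current SUD treatment a condition of entry.

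**Background care.** Section 3 says: "Both groups will be allowed to continue with whatever SUD treatment they are independently engaged in". TAU is not otherwise defined, and the study does not provide it.

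**Recruitment.** Section 4 uses the health system's recruitment registry and flyers at its own sites. It then adds: "Advertisements will also be placed on social media sites such as" two named platforms.

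**Analysis.** Section 9 gives Models 1-7 the same five covariates: age, sex, nicotine use, cardiovascular-acting medication and baseline past-month use. Versions with group in place of practice are stated for Models 4-7. No model has a term for SUD treatment, and no stratified randomization is described.

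**The concern.** Section 2 describes people in outpatient care. The entry criteria describe people in early recovery, whether or not they are in care. Someone with no current treatment can meet every stated criterion, be randomized, and be analysed under a label that includes TAU. In the experimental arm that person receives HRVB alone; in the control arm, only the momentary surveys.

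Two things are at stake.

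- **The claim.** The background presents HRVB as a possible addition to first-line SUD treatment, and the pilot's effect sizes are meant to inform a later trial. If an unknown share is untreated, the group effect is an average over treated and untreated people. It need not equal the effect of adding HRVB to outpatient care.
- **The practice-time models.** Most of Aim 2 rests on minutes of practice. Arm is randomized, but the amount of practice within the experimental arm is chosen by the participant. A person well engaged in treatment may both practise more and use less. With no treatment term, that shared cause can appear as a practice effect.

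**Working it through.** **1. The texts side by side**

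| Element | Section 2 and arm labels (Section 5) | Sections 3, 4 and 9 |
|---|---|---|
| Population | SUD, receiving outpatient TAU | SUD, age 18 or over, first year of a recovery attempt, two weeks abstinent |
| Treatment status | Present in everyone | Allowed, not required |
| Control condition | TAU only | Surveys plus any or no treatment |
| Treatment in the models | – | No term in Models 1-7 |

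Permission to continue existing treatment is satisfied by someone who has none, so Section 3 does not close the gap.

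**2. The plan's own figure**

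No stated figure is in dispute. For Aim 2b the plan gives a detectable R² of .10 at N = 100, 80% power and 5% alpha. A noncentral F test of the three practice terms among the eight in Model 7, with f² = R²/(1 − R²) and λ = f²·N, gives a detectable R² of 0.102 and power of 0.789 at R² = .10. The figure reproduces.

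**3. How many people fall outside the stated population**

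The documents give no share in treatment, q, so a range is assumed. The number in treatment is 120 × q.

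- q = 0.90: 108 in, 12 out
- q = 0.75: 90 in, 30 out
- q = 0.70: 84 in, 36 out (70 × 0.3 = 21 and 50 × 0.3 = 15)
- q = 0.50: 60 in, 60 out

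**4. What this could do to the group effect**

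Suppose, for illustration, a standardized effect of 0.5 in treated people and g × 0.5 in untreated people. The average effect is 0.5 × [q + (1 − q)g].

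| q | g = 1 | g = 0.5 | g = 0 |
|---|---|---|---|
| 0.90 | 0.50 | 0.475 | 0.45 |
| 0.75 | 0.50 | 0.4375 | 0.375 |
| 0.50 | 0.50 | 0.375 | 0.25 |

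If the effect does not depend on treatment, nothing changes. If it is larger without treatment, the shift goes the other way. The plan cannot tell these cases apart.

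**5. Chance imbalance between arms**

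The 95% range for the difference in treated share is 1.96 × √[q(1 − q)(1/70 + 1/50)].

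- q = 0.70: 1.96 × √(0.21 × 0.0343) = 0.166
- q = 0.50: 1.96 × √(0.25 × 0.0343) = 0.181

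If treatment shifts the outcome by 0.3 to 0.5 SD (assumption), a 0.166 imbalance moves the group difference by 0.166 × 0.3 = 0.05 SD to 0.166 × 0.5 = 0.08 SD. Sampling error of the group difference is 1.96 × √(1/70 + 1/50) = ±0.36 SD. The imbalance is minor beside it.

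**6. Confounding of practice time**

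Take the simplest version of Model 7: one practice term, no other covariates, and no true practice effect. The spurious correlation of practice with outcome is then r(practice, treatment) × r(treatment, outcome), and the spurious R² is its square. To produce the plan's benchmark of .10 from nothing, the product must reach √.10 = 0.316; if the two correlations are equal, each is √0.316 = 0.56. Treatment alone would therefore have to be a strong confounder to create the whole benchmark. Weaker correlations would still inflate it in part. Controls are all coded 0, so this correlation can arise only within the experimental arm.

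**7. Cost of a covariate**

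By the method in step 2, power at R² = .10 is 0.790 with three model terms, 0.789 with eight and 0.789 with nine. One more term costs almost nothing.

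**The case against.** The strongest reply is that TAU here means whatever care people happen to have, which is a common pragmatic form of usual care, and Section 3 says as much. The numbered aims (1, 2a, 2b) do not mention TAU, and the addition to first-line treatment is a rationale in the background, not a stated conclusion. That is fair for the numbered aims. It does not resolve the overarching aim sentence, which says participants are receiving outpatient treatment, nor the hypothesis and arm labels built on it.

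Four stronger readings are tempting, and the documents do not support them.

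- **That untreated people will be enrolled.** The text permits it but does not show it. The content of the phone screen is not itemized, so a treatment question there is neither stated nor ruled out.
- **That recruitment as a whole points outside care.** The flyers go up at health-system sites. Only the social media route clearly reaches people outside care.
- **That the group comparison is biased.** Randomization keeps it unbiased on average. Chance imbalance is already part of the standard error and, by step 5, is small in a pilot that says its power is limited.
- **That treatment status is not collected.** Section 6 allows about 45 minutes of intake questionnaires without listing them. Only its absence from the planned models can be shown.

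**Conclusion.** The point holds in a limited form. Sections 2 and 5 describe HRVB + TAU versus TAU only in people receiving outpatient treatment. Sections 3 and 4 admit people with or without treatment, and Section 9 does not account for the difference. The contrast named is therefore not guaranteed to be the contrast enrolled.

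The consequences are two: the population for which the result can be claimed, and possible confounding in the practice-time Models 1-7. The size of the first depends on the untreated share and on whether the effect differs by treatment, neither of which the documents give. At 10% to 50% untreated, 12 to 60 of the 120 participants fall outside the stated population. The second cannot be sized from the documents; in the simple case worked above, treatment alone would need correlations of about 0.56 with both practice and outcome to produce the full .10 benchmark. The pilot can run, but the wording and models should be aligned before its effect sizes are read as evidence for HRVB added to outpatient treatment.

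**What to change.** 1. Reconcile Sections 2 and 4. Reword the aim, hypothesis and arm labels to adults in early recovery with or without current SUD treatment, and say what TAU covers.
2. Record current outpatient SUD treatment (yes/no) at screening or baseline. If an intake questionnaire already captures it, name the item.
3. Add that baseline variable as a covariate in Models 1-7 and in the stated group versions of Models 4-7.
4. Report the group effect in the treated subset as a supportive estimate for HRVB + TAU. It will be less precise: at an assumed 30% untreated, the subset is about 49 versus 35, and its 95% half-width is 1.96 × √(1/49 + 1/35) = ±0.43 SD, against ±0.36 SD for the full sample.

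The cost is one question, one model term with almost no loss of power, and a claim that is broader and less specific than an addition to treatment. A baseline yes/no item will not capture changes in treatment during the 8 weeks or how engaged a person is, so some confounding of practice time may remain and should be stated as a limitation.

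### Models 1-3 carry no term for on-study substance use, so if practice changes around a lapse the affect and craving coefficients are confounded, in either direction

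*Combined protocol and SAP*

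**What the plan says.** Section 4 (Participants) requires "at least two weeks of abstinence from alcohol and other drugs immediately prior to study participation". Its stated purpose begins "To reduce the likelihood of acute substance withdrawal symptoms influencing affect and physiological indices, participants will be required". The requirement is placed at entry and nowhere else.

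Section 2 hypothesises a "lower alcohol/drug use lapse rate" with HRVB, so on-study use is expected. Section 3 has both groups complete "2x daily ecological momentary assessment of affect and substance use".

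In Section 9, Aim 2a, "we will explore the effects of day-level HRVB practice earlier in the day (i.e., lagged) on subsequent day-level negative affect" and on the other outcomes. For Models 1-3, "the dependent variables will be day-level negative affect scores, day-level craving scores, and day-level positive affect scores". The predictors are lagged scheduled minutes, lagged in-the-moment minutes and their product, "controlling for age, sex, nicotine use (yes/no), medications known to affect the cardiovascular system (yes/no), and baseline past-month AOD use". All five covariates are person-level. The plan states no term for on-study use, time since use or lagged affect, and no exclusion or sensitivity analysis for surveys after a lapse. On-study use appears only as an outcome, in Models 4-7.

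A version with group in place of practice is stated for Models 4 to 7 but not for Models 1-3.

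**The concern.** The protocol itself treats withdrawal after use as something that can influence affect, and controls it only before the study starts. During the study the same influence can enter the outcome of Models 1-3. The negative affect index includes guilt and craving, items likely to move with a lapse.

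That alone does not bias the practice coefficients. Bias needs a second link: practice must also change around use. Scheduled sessions may plausibly be missed during a lapse. In-the-moment practice may rise, because the device prompts when it infers stress (Section 1) and participants are encouraged to use it to regulate negative affect (Section 3). With both links present and use omitted, the two coefficients can be pushed in opposite directions. Aim 2 sets out to separate these two kinds of practice, and Section 9 says the effect sizes will inform the next trial. Because no group version of Models 1-3 is stated, the affect results have no stated randomised contrast to fall back on.

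**Working it through.** **The plan's own figure.** Aim 2a claims more than 99% power in Models 1-6 with r = 0.15, 5% alpha and 8,300 observations, assuming conditional independence. Fisher z: atanh(0.15) × √(8,300 − 3) − 1.96 = 0.1511 × 91.09 − 1.96 ≈ 11.8, so power is about 1.00. It reproduces on its own assumption. (100 × 42 × 2 is 8,400; the difference is immaterial here.) There is no stated figure for post-lapse confounding to check.

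**Inputs.** From the documents: 70:50 allocation, up to 84 surveys each, practice at t-1 predicting affect at t. Not in the documents, hence assumed: how often use occurs, how far affect shifts, and how practice changes. The true practice effect is set to zero throughout.

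**Sign and size by hand.** Let π be the share of surveys in use, γ the affect shift while using, p0 and p1 the chance of a session when not using and when using, and ρ the survey-to-survey correlation of use. For a within-person fit over T surveys:

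bias ≈ γ × ρ × π(1 − π)(p1 − p0) / [p(1 − p)] × w

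where p is the average session chance and w = 1 − (1/T)(1 + ρ)/(1 − ρ) is the within-person share of the variance in use.

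Take use starting with chance 0.01 per survey and continuing with chance 0.85. Then π = 0.01/0.16 = 0.0625, ρ = 0.85 − 0.01 = 0.84 and w = 1 − (1/84)(1.84/0.16) = 0.863.

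- Scheduled, 60% falling to 20%, γ = 0.6 SD: p = 0.575; 0.6 × 0.84 × 0.0586 × (−0.4)/0.244 × 0.863 ≈ −0.042 SD per session. Simulation gave −0.040.
- In-the-moment, 30% rising to 50%: p = 0.3125; 0.6 × 0.84 × 0.0586 × 0.2/0.215 × 0.863 ≈ +0.024 SD, toward harm. Simulation gave +0.02 to +0.035 SD over about 6-11% use, with 12-24% falsely significant.
- p1 = p0: zero.

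**Simulated false-positive rates.**

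1. Affect shifts while using (70/50 participants, 84 surveys, 600 trials per scenario, nominal 2.5% toward benefit). Use in 3-11% of surveys, shift 0.3-0.6 SD, scheduled sessions falling from 60% to 20%: false benefit 0.01-0.07 SD per 5-minute session, significant in 6-68%. If sessions fall only to 40% (6% use, 0.6 SD): 10%. If they do not fall: 3.5%. With use at t-1 added: 1.5-2.5%.
2. Affect stays worse for a window after a lapse (100 participants, 200 runs per scenario, two-sided nominal 5%). Window covering 6-37% of surveys, shift 0.5 or 1.0 within-person SD, scheduled practice down 30-60%: 0.02-0.27 SD per 5 minutes, significant in 11-100%. Practice unchanged: 3-7%. In-the-moment practice up by 1 minute: +0.01 to +0.08 SD per 2 minutes toward harm, significant in 10-99%. Adding an indicator for the true window: 4-10% for scheduled practice.
3. Practice responds to use reported one survey earlier (500 trials per scenario): 5%, 18% and 54% false benefit at 3%, 6% and 11% use. Adjusting for use before the practice interval: 3-4%. No fall in practice: 3%. When in-the-moment practice also rose from 40% to 70% at 6% use, there was 22% false benefit on scheduled practice and 15% false harm on in-the-moment practice; adjustment removed both.

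**Against the plan's benchmark.** The largest average spurious semi-partial R² for scheduled practice in any scenario of set 2 was 0.0084, about one twelfth of .10.

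**Which covariate.** Under the set 1 mechanism (0.6 SD, sessions falling from 60% to 20%), false benefit was:

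| Adjustment | about 6% use | about 11% use |
|---|---|---|
| None | 31% | 68% |
| Any use in preceding 14 days | 29% | 61% |
| Use at t-1 | 4% | 2% |

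A separate run with main effects only gave 30%, 22% and 2.8% at 6% use, and 74%, 66% and 3.5% at 11%. At 6% use the 14-day indicator moved the bias only from −0.040 to −0.034 SD, leaving 0.034/0.040 = 85% of it.

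**The case against.** Four points can be made for the plan.

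- **Direction is not documented.** A reader might infer that the bad days after a lapse will be credited to missed practice, so that the error favours HRVB. The documents do not support that: they say nothing on how practice changes after use, and what they say about prompted, as-needed practice points toward a rise. This stands, and the point is confounding of unknown sign.
- **The pilot will be read on effect sizes.** Section 9 sets its benchmark at a semi-partial R² of .10 for practice time. A reader might infer that a lapse artefact could produce a declared benefit; the figures above are far too small for that. This stands too. But Aim 2a also predicts coefficient direction and quotes power at 5% alpha, and those readings remain exposed.
- **The entry rule is an entry rule.** It does not say affect is distorted for 14 days after every lapse. True, so 14 days is a borrowed window and cannot carry the main adjustment.
- **Use may lie on the causal path.** Use occurring after the practice at t-1 may be a consequence of it, and adjusting for it would remove part of any real effect. Use reported before that practice cannot be its consequence. Timing the covariate correctly answers the objection for the lagged coefficient.

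Nor is the information missing: use is recorded at the surveys. Only the models leave it out.

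**Conclusion.** The gap is documented: a distorter of affect that the protocol names is controlled at entry and left out of Models 1-3 thereafter. Whether it biases the results depends on practice changing around use, which the documents neither state nor exclude. If it does, false-positive rates can rise from near nominal to well over half under the assumed ranges, toward benefit for scheduled practice that falls and toward harm for in-the-moment practice that rises. If it does not, there is no bias. The declared .10 criterion is not at risk in any scenario tried.

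The simulations use within-person fits. Models 1-3 as written state no centring, so their coefficients would mix within-person and between-person differences. Confidence is high on the omission and moderate on its consequence. The change is worth making because it is cheap, not because the trial's conclusion hangs on it.

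**What to change.** In Models 1-3, add time-varying terms for recent use reported before the t-1 practice interval: use at the most recent prior survey, and time since last reported use. Do not rely on a single any-use-in-14-days indicator, which leaves most of the bias when affect shifts mainly during use. Define in the SAP which survey precedes which practice interval. Do not adjust for use occurring after the practice interval, and keep these terms out of any randomised-group version, where use would be a mediator.

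As a sensitivity analysis, repeat Models 1-3 without surveys that follow reported use within 14 days. State that the window is borrowed from the entry rule and that the analysis conditions on a post-randomisation event that HRVB is hypothesised to change.

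Cost: SAP wording and extra terms built from data already collected, with slightly wider intervals. Some bias will remain if use between surveys is misreported or mistimed, or if practice responds to use within the same interval, which a term limited to earlier use captures only in part. The two terms were not simulated together as specified here; the supporting figures are for the single prior-use term.
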